1. PROJECT TITLE

Intercostal Cryoneurolysis following Traumatic Rib Fractures

4. ESTIMATED DURATION OF THE STUDY

Three years (including follow-up and analysis)

5. LAY LANGUAGE SUMMARY OR SYNOPSIS (no more than one paragraph)

Rib fractures are one of the most common injuries in trauma patients. These fractures are associated with significant pain as well as decreased ability to inspire deeply or cough to clear secretions, which together lead to pulmonary complications and a high degree of morbidity and mortality. Peripheral nerve blocks as well as epidural blocks have been used with success to improve pain control in rib fracture patients and have been associated with decreased pulmonary complications and improved outcomes. However, a single-injection nerve block lasts less than 24 hours; and, even a continuous nerve block is generally limited to 3-4 days. The pain from rib fractures usually persists for multiple weeks or months. In contrast to local anesthetic-induced nerve blocks, a prolonged block lasting a few weeks/months may be provided by freezing the nerve using a process called "**cryoneurolysis**". The goal of this study is to evaluate the potential of cryoanalgesia to decrease pain and improve pulmonary mechanics in patients with rib fractures.

6. SPECIFIC AIMS

The ultimate objective of the proposed line of research is to determine if cryoanalgesia is an effective treatment for pain associated with rib fractures; and, if this analgesic modality improves pulmonary mechanics measured with incentive spirometry.

Specific Aim 1: To determine if, compared with current and customary analgesia for rib fracture(s), intercostal nerve cryoneurolysis improves maximum inspiratory volume.

Hypothesis 1a: The maximum inspired volume will be significantly *increased* on the day following the procedure [primary endpoint] as well as at other time points following the procedure [secondary end points] with intercostal cryoanalgesia as compared single-injection local anesthetic-based intercostal nerve blocks [measured with an incentive spirometer].

Hypothesis 1b: The maximum inspired volume as a percentage of the baseline will be significantly *increased* on the day following the procedure [secondary endpoint of greatest interest], as well as at other time points following the procedure [secondary end points] with intercostal cryoanalgesia as compared with single-injection local anesthetic-based intercostal nerve blocks [measured with an incentive spirometer].

Specific Aim 2: To determine if, compared with current and customary analgesia, intercostal nerve cryoneurolysis decreases the pain associated with rib fracture(s).

Hypothesis 2a: The severity of rib fracture pain at rest will be significantly decreased within the 12 months following the procedure with intercostal cryoneurolysis as compared with subjects receiving single-injection local anesthetic-based intercostal nerve blocks [measured using the Numeric Rating Scale for pain].

Hypothesis 2b: The severity of rib fracture pain when using the spirometer or coughing will be significantly decreased within the 12 months following the procedure with intercostal cryoneurolysis as compared with subjects receiving single-injection local anesthetic-based intercostal nerve blocks [measured using the Numeric Rating Scale for pain].

Hypothesis 2c: The incidence of chronic pain will be significantly decreased 6 and 12 months following a rib fracture with intercostal cryoneurolysis as compared with subjects receiving single-injection local anesthetic-based intercostal nerve blocks [measured using the Numeric Rating Scale for pain].

Hypothesis 2d: The severity of chronic pain will be significantly decreased 6 and 12 months following a rib fracture with intercostal cryoneurolysis as compared with subjects receiving single-injection local anesthetic-based intercostal nerve blocks [measured using the Numeric Rating Scale for pain].

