For subjects at the University of Florida, their anthropomorphic, baseline, procedure, and post-procedure data will be recorded on the same case report form as at the University California San Diego and faxed to the investigators at UC San Diego following the procedure. These faxed documents will remain in electronic form (eFax) on the Principal Investigator's password-protected, encrypted, UCSD-owned MacBook computer. Investigators at UC San Diego will do all of the follow-up data collection by phone for subjects at both treatment centers.

Outcome measurements (end points). Anesthesia providers will perform all measures and assessments, which will include:

1. **Pain:** measured on the 11-point NRS of pain intensity
2. **Opioid consumption**
3. **Pain interference:** measured using the Brief Pain Inventory (which includes the pain scores of #1 above)
4. **Sleep disturbances (#):** due to pain
5. **Pulmonary Mechanics:** measured by the inspired volume on a handheld incentive spirometer based on the American Association of Respiratory Care (AARC) clinical practice guideline.⁷ The best of three measurements will be recorded as the maximum inspired volume.

Statistical Analysis: The primary endpoint is the maximum inspired volume measured by incentive spirometry the day following treatment. There is no accepted minimal clinically-relevant change in incentive spirometry volume. However, the median (IQR) of inspired volume for patients with rib fracture(s) is 1250 (750-1750) mL,⁸ and, ISV<1000 mL is associated with an increased risk of acute respiratory failure.⁸ We will therefore use the difference between 1250 and 1000 (250 mL) as the minimal clinically-relevant difference. However, there is high variability in the reported increase in inspired volume with various regional analgesic interventions such as continuous intercostal nerve blocks⁹ and serratus plane blocks,¹⁰ and we will therefore increase our enrollment to account for an unpredicted increase in variability or non-normal data distribution.

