But, assuming a normal distribution, the interquartile range is approximately 1.35 standard deviations (SDs). Therefore an interquartile range of 250-50 = 200 mL (Hernandez et al. 2019) corresponds to, approximately, an SD of $200/1.35 = 148$ mL. Assuming this SD of 148 mL, a sample size of n=7 per group provides 80% power to detect a group difference of d=250 mL per group with two sided Type 1 Error 5%. To allow for a larger-than-anticipated SD, we will enroll 10 subjects per group with an evaluable primary outcome measure (n=20 for both groups combined). Accounting for drop-outs, we request a maximum enrollment of 30 subjects.

"Continuous data will be summarized with mean, SDs, medians, quartiles, and ranges; and displayed with box-and-whisker plots by group and in aggregate. Key baseline characteristics will be

tested between groups using two-sample t-tests, and summarized with Cohen's D, for continuous measures; and Fisher's Exact test for categorical variables. The primary outcome is maximum incentive spirometry volume (ISV) measured in mL on POD 1. The group difference will be tested using Welch's two-sample test. Secondary outcomes will also be tested with the two-sample t-test. No multiplicity adjustments will be applied for these secondary outcomes. The Wilcoxon signed-rank test will be used as a sensitivity analysis. Secondary analyses will include a Mixed Model of Repeated Measures with fixed-effects for time, time-by-group, unilateral vs bilateral, and the number of fractures. The model will treat time as a categorical variable and will assume a compound symmetric correlation and heterogeneous variance with respect to time. The estimated mean difference between groups at the final scheduled timepoint will be the parameter of interest and will be tested using Kenward-Roger degrees of freedom. Out-comes only measured at baseline and a single follow-up timepoint will be analyses with Analysis of Covariance (ANCOVA). The dependent variable will be change from baseline, and covariates will include group, baseline outcome, unilateral vs bilateral, and the number of fractures. Missing data is not expected due to the short follow-up in this study. However, if missing data issues arise, we will use multiple imputation which is robust to covariate-dependent Missing at Random, and tipping point analyses under various Missing Not at Random assumptions."

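### Hypothesis 1b tests Day 1 volume as a percentage of baseline by an unadjusted t-test, which generally has less power than baseline-adjusted ANCOVA and leaves chance baseline imbalance in the result

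*Combined protocol and SAP*

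**What the plan says.** Section 6 (Specific Aims), Hypothesis 1b: "The maximum inspired volume as a percentage of the baseline will be significantly" increased on the day after the procedure. It is labelled the "secondary endpoint of greatest interest", and the same measure is a secondary endpoint at the other time points.

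Section 9 (Research Design and Methods, Statistical Analysis) sets the test: "Secondary outcomes will also be tested with the two-sample t-test". Its other rules do not give a baseline-adjusted Day 1 result for spirometry:

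- **ANCOVA.** "Out-comes only measured at baseline and a single follow-up timepoint will be analyses with Analysis of Covariance (ANCOVA"). The Study Overview in the same section schedules spirometry on Days 1, 2 and 7, and later if the subject has a spirometer, so this rule does not reach it.
- **Repeated measures.** The model is a "Mixed Model of Repeated Measures with fixed-effects for time, time-by-group, unilateral vs bilateral, and the number of fractures". Baseline volume is not among the listed effects, and "The estimated mean difference between groups at the final scheduled timepoint will be the parameter of interest", which is not Day 1.
- **Sensitivity analysis.** "The Wilcoxon signed-rank test will be used as a sensitivity analysis". As named, this is a paired or one-sample test.

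Baseline spirometry is collected on Day 0. Randomisation is stratified by centre and by unilateral or bilateral fractures, not by baseline volume.

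**The concern.** A percentage of baseline looks like a baseline adjustment, and readers will take it as one. It works as one only if Day 1 volume is proportional to baseline. If subjects with low baselines gain relatively more, through a roughly constant gain in mL or through regression to the mean, the percentage stays negatively related to baseline. Subjects with small baselines then contribute large and variable percentages, and an arm that starts lower by chance looks better.

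This is the trial's second-ranked result and the only Day 1 spirometry result that refers to the subject's own starting point. With 10 subjects per arm and no stratification on baseline volume, sizeable chance imbalance is likely. At stake are some of the power that the data could give and a conditional shift that the percentage appears to have removed.

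**Working it through.** **1. The plan's own figure.** Section 9 takes an IQR of 200 mL, so SD = 200/1.35 = 148 mL, and states 7 per group for 80% power at 250 mL. A noncentral-t calculation gives 6.6, rounded up to 7, with power 82.6% at 7 and 94.6% at 10 per group. The figure reproduces. It concerns the raw Day 1 volume of the primary endpoint; the plan states no figure for Hypothesis 1b.

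**2. Spread of baseline.** Section 9 also says that "the median (IQR) of inspired volume for patients with rib fracture(s) is 1250 (750-1750) mL". Hence SD = (1750 − 750)/1.35 = 741 mL. At 10 per arm the standard error of the baseline difference is 741 × √(2/10) = 331 mL. If the SD of level were only 148 mL, it would be 148 × √(2/10) = 66 mL.

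**3. Why the percentage does not remove baseline.** Write Day 1 volume as Y = a + bX + e, with X the baseline. Then 100·Y/X = 100b + 100a/X + 100e/X. With a > 0 the percentage falls as X rises; with a = 0 that term vanishes. For example, take b = 1 and baselines at the two quartiles:

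| Quantity | X = 750 mL | X = 1750 mL |
|---|---|---|
| Constant gain of 150 mL | 20.0 points | 8.6 points |
| Effect of 250 mL | 33.3 points | 14.3 points |
| SD of change of 148 mL | 19.7 points | 8.5 points |

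Both signal and noise are larger at low baselines.

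**4. Power.** Simulation at 10 per arm, two-sided 5%, with a lognormal baseline matching quartiles 750 and 1750 and floored at 250 mL. Control gains, correlations and the SD of 300 mL are assumptions, because the documents do not give them.

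| Scenario | t-test on percentage | Log-scale ANCOVA |
|---|---|---|
| +250 mL, SD of change 148, control gain 0 | 78% | 85% |
| Same, control gain 75 mL | 67% | 84% |
| Same, control gain 150 mL | 55% | 84% |
| +250 mL, SD of change 300 | about 26–30% | 32–33% |
| 50% multiplicative gain, log-scale correlation 0.5 | 21% | 33% |
| Same, correlation 0.85 | 66% | 70% |

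Repeat runs differ by a few points. At SD 300 with zero control gain, one run put the two tests level at 33%.

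On the additive mL scale, mL-scale ANCOVA does better still: 93% against 84–85% for the log version at SD of change 148, and about 40% against 33% at SD 300.

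**5. Null behaviour.** Across these and other settings the percentage t-test rejected in about 3 to 5% of null trials. Given a baseline imbalance of one standard error (331 mL), the percentage difference moved by about 0 to 11 points toward the lower-starting arm. It was near 0 with no control gain and an SD of change of 148 mL, and largest at low correlation. The ANCOVA estimate was uncorrelated with the imbalance.

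**6. Other comparators.** In a separate simulation with normal data and an additive effect, the percentage was below mL-scale ANCOVA in every setting, by under 1 to about 17 points. Where Day 1 was exactly proportional to baseline, it was about level with log-scale ANCOVA (for example 47% against 46%) and mostly equal to or better than mL-scale ANCOVA.

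**The case against.** Several stronger readings are tempting, and the documents do not support them.

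- **That the endpoint is biased.** It is not. Randomisation leaves no systematic bias, and type I error is held. The shift exists only given a chance imbalance, and it vanishes under proportionality.
- **That the percentage loses power outright.** This is true only against baseline-adjusted ANCOVA. Against the plan's own unadjusted Day 1 comparison, the percentage is about level or better at a correlation of 0.7 and clearly better at 0.8 to 0.9.
- **That the loss is near 30 points.** That needs a control gain of 150 mL. Section 5 puts a single-injection block at under 24 hours, and section 7 reports intercostal blocks resolving in as little as six. A control gain near zero on Day 1 is therefore at least as plausible, and there the loss is 7 points (85 − 78).
- **That the skew is known to be severe.** The quoted quartiles are symmetric about 1250 mL, whereas the lognormal used here has its median near 1,140 mL. The eligibility criteria (1 to 6 fractures, no flail chest or chest tube, able to perform spirometry) may also thin the low tail. Skew is mild if the SD is 148 mL. A normal baseline does not remove the loss, however: it gave about 16 points at zero control gain and 38 at 150 mL.

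If 148 mL is an SD of change (inferred, not stated) and 741 mL the SD of level, with equal variances, the correlation is 1 − 148²/(2 × 741²) = 0.98. The percentage then has 79–96% power against 92–95% for mL-scale ANCOVA, so the loss can be small.

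The Wilcoxon sensitivity analysis, read as a two-group rank test, would help with skew but not with imbalance. Even if baseline entered the repeated-measures model as a time point, the named contrast is the final one. What stands is that no planned Day 1 analysis adjusts for baseline.

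**Conclusion.** The concern holds in a limited form. The second-ranked endpoint rests on an unadjusted test of a ratio, and no baseline-adjusted Day 1 analysis of spirometry is planned. Against log-scale ANCOVA the loss ranges from negligible, when Day 1 volume is close to proportional to baseline, to about 29 points (84 − 55) in the least favourable lognormal scenario. The conditional shift from one standard error of imbalance is about 0 to 11 percentage points.

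These sizes rest on the 741 mL spread applying to this trial's subjects and on assumed correlations and control gains, so no single figure should be quoted as the loss. The primary analysis and its sample size are untouched. The change is worth making because the needed baseline is already collected.

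**What to change.** Make the inferential analysis for Hypothesis 1b an ANCOVA of Day 1 volume on treatment group, baseline volume and the stratification factors (centre, unilateral or bilateral). Fix the scale before unblinding:

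- **Log scale** (log Day 1 on log baseline) reports an adjusted ratio of geometric means with its 95% CI. It keeps the relative meaning of Hypothesis 1b.
- **mL scale** reports an adjusted mean difference with its 95% CI. It matches the plan's 250 mL effect and had more power when the effect was additive.

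Use the same model at the other Hypothesis 1b time points, and show raw percentages of baseline descriptively.

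The cost is a few sentences in section 9 and no new data. The small downside is that the reported effect becomes an adjusted ratio or an adjusted mL difference instead of a difference in mean percentages.

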7. BACKGROUND AND SIGNIFICANCE

[figure not shown]
Rib fractures represent a significant source of morbidity in trauma patients, with approximately 10% of trauma patients presenting with rib fractures.¹ Pain from rib fractures is associated with decreased ability to cough and inspire deeply, predisposing patients to atelectasis and pulmonary complications. Neuraxial blocks, both thoracic epidurals and paravertebral blocks, have been associated not only with decreased pain, but also decreased pulmonary complications and overall mortality in patients with rib fractures.² Furthermore, intercostal nerve blocks with local anesthetic have been shown to improve pain scores, peak expiratory flow rates, and arterial oxygen saturation on room air.³ However, intercostal nerve blocks are not without risk and incidence of pneumothorax has been reported as 1.4% for each individual intercostal nerve that is blocked.⁴ Although it is possible that the use of in-plane ultrasound guidance may decrease the risk of pneumothorax, this has not been evaluated. Additionally, intercostal blocks with bupivacaine have been reported to resolve in as little as six hours,⁵ likely due to the high vascularity and consequent uptake of local anesthetic from the intercostal space.

An alternative analgesic technique is cryoneurolysis, consisting of the application of exceptionally low temperatures to *reversibly* ablate peripheral nerves, resulting in temporary pain relief termed “*cryoanalgesia*”.⁶ The intense cold temperature at the probe tip produces Wallerian degeneration—a reversible breakdown of the nerve axon—subsequently inhibiting transmission of afferent and efferent signals. Because the nerve endoneurium, perineurium, and epineurium remain

intact, the axon regenerates along the exoskeleton at a rate of approximately 1-2 mm/day. While cryoneurolysis of peripheral nerves through surgical incisions has been commonly used to treat pain since 1961, the development of cryo probes that may be inserted percutaneously promise a revolution in the use of this modality.

The combination of newly-designed narrow-gauge probes (upper right) and ultrasound now make percutaneous cryoanalgesia as simple as placing a peripheral nerve block: the probe tip is inserted adjacent to the target nerve under ultrasound guidance, and a series of 2-minute freezing cycles are administered followed by probe withdrawal. ***The procedure is essentially the same as placing an ultrasound-guided peripheral nerve block; however, instead of injecting local anesthetic, a gas circulates through the probe, inducing cold at the tip and freezing the target nerve.***

Nothing remains within the patient and there is no external equipment to prepare or manage. Importantly, cryoneurolysis and the probes are already approved by the United States Food and Drug Administration for the treatment of acute and chronic pain, so no additional regulatory approval is required for the proposed clinical trial.

Theoretical benefits of cryoneurolysis include an ultra-long duration of pain control without opioid involvement, no catheter management/removal (reducing infection risk), the lack of an infusion pump and anesthetic reservoir to carry, an extraordinarily-low risk of infection (approaching zero), and no risk of local anesthetic toxicity, catheter dislodgement or leakage. With a single 8-minute percutaneous cryoneurolysis procedure consisting of several freeze/defrost cycles, a truncation of sensory nerve conduction is induced for 6-8 weeks, with the complete restoration of nerve structure and function following remyelination. Cryoneurolysis offers the possibility of potent, side effect-free analgesia outlasting the surgical pain, and obviating the need for postoperative opioids.

8. PROGRESS REPORT

We have performed several cases in which cryoneurolysis was performed after rib fractures producing significant and long-lasting pain relief. All patients experienced significant pain relief immediately, continuing for at least 2 weeks post-intervention. Numeric Rating Scale pain scores were consistently improved from before the procedure for multiple weeks. No adverse events associated with cryoanalgesia were reported in any of the patients.

9. RESEARCH DESIGN AND METHODS

The cryoneurolysis procedure will be compared with our current UCSD standard practice.

Study Overview

Day 0

Baseline pain levels and spirometry

Subjects randomized and cryoneurolysis/sham procedure administered
Post-block pain levels and spirometry repeated

Days 1, 2, 7	Pain levels, opioid consumption, sleep disturbances due to pain, and incentive spirometry values collected [day of discharge recorded]
Months 0.5, 1, 1.5 , 2 3, 6, and 12	Pain levels, opioid consumption, sleep disturbances due to pain, and pain interference collected [if subject has spirometer available]

Subjects will be individuals who present to one of the UCSD hospitals with rib fracture(s) and significant pain. The University of Florida will be following the same protocol and the subjects from both institutions will be combined for the analysis. Those who consent to participate in this study will have standard ultrasound-guided intercostal nerve blocks administered with ropivacaine 0.5% (with epinephrine), 3 mL/level of each fracture rib as well as one level above and one level below.

Treatment group assignment (randomization). Subjects will be allocated to one of two possible treatments stratified by treatment center and unilateral vs. bilateral fractures:

1. **active cryoneurolysis (*sham local anesthetic intercostal blocks*)**
2. **sham cryoneurolysis (*active local anesthetic intercostal blocks*)**

Computer-generated randomization lists will be used to create sealed, opaque randomization envelopes with the treatment group assignment enclosed in each envelope labeled with the randomization number.

The specific intercostal nerves targeted will depend on the injury site. The treatment sites will be cleansed with chlorhexidine gluconate and isopropyl alcohol. Using the optimal ultrasound transducer for the specific anatomic location and subject anatomy (linear vs curvilinear array), the target nerves will be identified in a transverse cross-sectional (short axis) view. The intercostal nerve of each fractured rib as well as the level above and below will be treated with the protocol below:

Intercostal nerve block procedure: The target nerve will be visualized with ultrasound. Local anesthetic (1% lidocaine) will be used to infiltrate the skin and underlying muscle at each entry point. A 20 g Tuohy needle will be introduced through the skin wheel and along the anesthetized muscle tract. For subjects randomized to active cryo, 3 mL of normal saline will be injected into the muscle superficial to the nerve; and for subjects randomized to sham cryo, 3 mL of ropivacaine 0.5% (with epinephrine) will be injected perineurally to provide the intercostal nerve block.

Cryoneurolysis procedure: Cryoneurolysis probes are available for a console neurolysis device (PainBlocker, Epimed, Farmers Branch, Texas) that either (1) pass nitrous oxide to the tip inducing freezing temperatures; or, (2) vent the nitrous oxide at the base of the probe so that no gas reaches the probe tip, resulting in no temperature change. The latter is a sham procedure since without the temperature change, no ice ball forms and therefore the target nerve is not affected. An angiocatheter/introducer will be inserted beneath the ultrasound transducer and directed until the probe tip is immediately adjacent to the target nerve. The angiocatheter needle will be removed, leaving the angiocatheter through which the appropriate Epimed probe will be inserted until it is adjacent to the target nerve. The cryoneurolysis device will be triggered using 2 cycles of 2-minute gas activation (active or sham) separated by 1-minute defrost periods. For active probes, the nitrous oxide will be deployed to the tip where a drop in temperature to -70°C will result in cryoneurolysis. For the sham probes, the nitrous oxide will be vented prior to reaching the probe shaft, resulting in a lack of perineural temperature change.

The process will be repeated with the same treatment probe for any additional nerves (e.g., all nerves will receive either active cryoneurolysis or sham/placebo, and not a mix of the two possible treatments).

For subjects at the University of Florida, their anthropomorphic, baseline, procedure, and post-procedure data will be recorded on the same case report form as at the University California San Diego and faxed to the investigators at UC San Diego following the procedure. These faxed documents will remain in electronic form (eFax) on the Principal Investigator's password-protected, encrypted, UCSD-owned MacBook computer. Investigators at UC San Diego will do all of the follow-up data collection by phone for subjects at both treatment centers.

Outcome measurements (end points). Anesthesia providers will perform all measures and assessments, which will include:

1. **Pain:** measured on the 11-point NRS of pain intensity
2. **Opioid consumption**
3. **Pain interference:** measured using the Brief Pain Inventory (which includes the pain scores of #1 above)
4. **Sleep disturbances (#):** due to pain
5. **Pulmonary Mechanics:** measured by the inspired volume on a handheld incentive spirometer based on the American Association of Respiratory Care (AARC) clinical practice guideline.⁷ The best of three measurements will be recorded as the maximum inspired volume.

Statistical Analysis: The primary endpoint is the maximum inspired volume measured by incentive spirometry the day following treatment. There is no accepted minimal clinically-relevant change in incentive spirometry volume. However, the median (IQR) of inspired volume for patients with rib fracture(s) is 1250 (750-1750) mL,⁸ and, ISV<1000 mL is associated with an increased risk of acute respiratory failure.⁸ We will therefore use the difference between 1250 and 1000 (250 mL) as the minimal clinically-relevant difference. However, there is high variability in the reported increase in inspired volume with various regional analgesic interventions such as continuous intercostal nerve blocks⁹ and serratus plane blocks,¹⁰ and we will therefore increase our enrollment to account for an unpredicted increase in variability or non-normal data distribution.

But, assuming a normal distribution, the interquartile range is approximately 1.35 standard deviations (SDs). Therefore an interquartile range of 250-50 = 200 mL (Hernandez et al. 2019) corresponds to, approximately, an SD of $200/1.35 = 148$ mL. Assuming this SD of 148 mL, a sample size of n=7 per group provides 80% power to detect a group difference of d=250 mL per group with two sided Type 1 Error 5%. To allow for a larger-than-anticipated SD, we will enroll 10 subjects per group with an evaluable primary outcome measure (n=20 for both groups combined). Accounting for drop-outs, we request a maximum enrollment of 30 subjects.

"Continuous data will be summarized with mean, SDs, medians, quartiles, and ranges; and displayed with box-and-whisker plots by group and in aggregate. Key baseline characteristics will be

tested between groups using two-sample t-tests, and summarized with Cohen's D, for continuous measures; and Fisher's Exact test for categorical variables. The primary outcome is maximum incentive spirometry volume (ISV) measured in mL on POD 1. The group difference will be tested using Welch's two-sample test. Secondary outcomes will also be tested with the two-sample t-test. No multiplicity adjustments will be applied for these secondary outcomes. The Wilcoxon signed-rank test will be used as a sensitivity analysis. Secondary analyses will include a Mixed Model of Repeated Measures with fixed-effects for time, time-by-group, unilateral vs bilateral, and the number of fractures. The model will treat time as a categorical variable and will assume a compound symmetric correlation and heterogeneous variance with respect to time. The estimated mean difference between groups at the final scheduled timepoint will be the parameter of interest and will be tested using Kenward-Roger degrees of freedom. Out-comes only measured at baseline and a single follow-up timepoint will be analyses with Analysis of Covariance (ANCOVA). The dependent variable will be change from baseline, and covariates will include group, baseline outcome, unilateral vs bilateral, and the number of fractures. Missing data is not expected due to the short follow-up in this study. However, if missing data issues arise, we will use multiple imputation which is robust to covariate-dependent Missing at Random, and tipping point analyses under various Missing Not at Random assumptions."

